Blood samples for assessing plasma drug concentrations will be obtained at a subset of sites from at least 24 patients in the treated group. On Week 1, a single predose blood sample will be taken within 2 hours prior to the start of administration of the first dose. Both predose and postdose samples will be taken on Weeks 40, 48, 60, 84, and 96 as follows: within 2 hours prior to the start of the infusion, and approximately 5 to 10 minutes, 1 to 2 hours, and 2 to 4 hours after completion of the infusion; at Weeks 48 and 96, samples will also be taken at the end of the infusion prior to flushing the infusion line. Postdose samples alone will be taken on Weeks 8, 16, 24, 32, and 72, approximately 5 to 10 minutes after the completion of the infusion (the approximate time of post-dosing maximum plasma concentration for eteplirsen). Additional post dose samples will be taken on Weeks 8 and 24, approximately 1 to 2 hours after the completion of the infusion and on Week 72 at 2 to 4 hours after the completion of the infusion.

DURATION OF STUDY:

Screening/Baseline Period: up to 10 weeks (not including time needed for genotyping if the patient has not previously been genotyped)

Treatment Period: at least 96 weeks Safety Extension: not to exceed 48 weeks

Safety Follow-up Period: 4 weeks following the last infusion

Total patient participation: approximately 158 weeks

NUMBER OF PATIENTS: Approximately 110 patients will be included in this study, including approximately 90 patients with a Baseline 6MWT distance between 300 and 450 meters (~70 patients in the treated group and ~20 patients in the untreated control group) and approximately 20 patients with a Baseline 6MWT distance >450 meters (~10 patients in the treated group and ~10 patients in the untreated control group).

INCLUSION/EXCLUSION CRITERIA:

Inclusion Criteria:

A patient must meet all of the following criteria to be eligible for this study.

- 1. Be a male with DMD and meet one of the following criteria:
 - Have an out-of-frame deletion that may be treated by exon 51 skipping (e.g., deletions of exons 45-50, 47-50, 48-50, 49-50, 50, 52, 52-63). These patients will be enrolled into the treated group.
 - Have an out-of-frame deletion that is not amenable to treatment by exon 51 skipping but is amenable to treatment by skipping other exons (i.e., whole exon deletions in which the

Sarepta Therapeutics Inc. [name] [contact]

NAME OF FINISHED PRODUCT

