a Patients may continue in the safety extension for up to 48 weeks, until the product is commercially available or until they can transition into a separate eteplirsen study.

b Early termination assessments are the same as Week 144 assessments.

c Full physical examination: general appearance, head, eyes, ears, nose, and throat (HEENT), heart, chest, abdomen, skin, lymph nodes, extremities, musculoskeletal, and neurological systems.

d Vital signs include blood pressure, heart rate, respiration, and oral temperature. On infusion days, vital signs will be measured prior to infusion and approximately 5 and 30 minutes after the end of the infusion. If the patient has not experienced an infusion reaction after the first year of treatment, vital signs may be reduced to pre-infusion and 30 minutes after the end of the infusion.

Table 5: Schedule of Events for Untreated Control Patients - Screening Through End of Study

Assessments	Up to	10 weeks	prior to Week 1ª				Olara		•. ah			
Study Period		ening p to -3w	Baseline -4w to Day -1&-2		(2-da	ay HS visi		rvation Po t Weeks 1		48, 72, an	nd 96)	
Week	1-day visit	2-day visit	2-day visit (3-5w after Screening at HS)	W1°	W4	W8	W12	W24	W36	W48	W72	W96/ ET ^b
Informed consent for screening at local site	X											
Informed consent for screening at HS (if different from local site)		HS										
Informed consent to participate as a control patient (no consent form needed at W12 if local is same as HS)				X			HS					
Assess inclusion/exclusion criteria	X	HS	HS									
Confirm eligibility ^d			X	X								
Medical history	X											
Full physical examination ^e	X			X	X		X	X	X	X	X	X
Brief physical examination ^e						X						
Vital signs ^f	X		HS	X	X	X	X	X	X	X	X	X
Weight	X			X	X	X	X	X	X	X	X	X
Safety laboratory assessments ^g	X ^h			$X^{h,i}$	X	X	X	X	X	X	X	X

Table 5: Schedule of Events for Untreated Control Patients - Screening Through End of Study, continued

Assessments	Up to	10 weeks	prior to Week 1ª				Ohga	rvation P	out o db				
Study Period		ening p to -3w	Baseline -4w to Day -1&-2		(2-da	ny HS visi	ts occur a			48, 72, an	d 96)		
Week	1-day visit	2-day visit	2-day visit (3-5w after Screening at HS)	W1°	W4	W8	W12	W24	W36	W48	W72	W96/ ET ^b	
Immunogenicity				Xi	X	X	X	X	X	X	X	X	
CCI													
Whole blood for DMD genotyping	X												
CCI													
Height (and ulnar length at HS visits)	X		HS				HS	HS	HS	HS	HS	HS	
6MWT ^j		HS	HS				HS	HS	HS	HS	HS	HS	
NSAA ^j			HS				HS	HS	HS	HS	HS	HS	
CCI													

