4. STUDY OVERVIEW

4.1. Study Design

This is an open-label, multicenter study to evaluate the efficacy and safety of eteplirsen in patients with genotypically confirmed DMD with exon deletions amenable to exon 51 skipping (eteplirsen-treated group), as compared with an untreated control arm of DMD patients amenable to exon skipping (untreated control group). Note that patients in the untreated control arm are not amenable to exon 51 skipping.

Patients will be evaluated for inclusion during a Screening/Baseline period of up to 10 weeks (not including time needed for genotyping if the patient has not been previously genotyped). Eligible patients for the eteplirsen-treated group will receive once weekly intravenous infusions of 30 mg/kg eteplirsen for 96 weeks, followed by a safety extension (not to exceed 48 weeks), until the product is commercially available or until patients can transition into a separate eteplirsen study. Eligible patients in the untreated control group will not receive treatment with eteplirsen but will complete selected study assessments through 96 weeks.

An overview of the study design through Week 96 is presented in Figure 1.

[figure not shown]

Figure 1 Overview of Study Design through Week 96

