4.4.2 Final Analysis

A final analysis of safety and efficacy will be conducted once the last patient completes the entire study and the resulting database is cleaned, quality assured, locked, and unblinded. All statistical analyses will be performed by or under the supervision of the Sponsor. All available data will be included in data listings and tabulations. Due to the small population size and large dropout rate of the untreated control group, only descriptive summaries will be presented. An external control dataset will be identified and used to evaluate the effect of eteplirsen treatment. The statistical methods for the identification and use of the external control dataset will be presented in a supplemental SAP.

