6. GENERAL STATISTICAL METHODS AND CONVENTIONS

6.1. General Methods

Summary statistics will be presented by treatment group, unless stated otherwise.

For continuous variables, descriptive statistics will include the number of patients with data to be summarized (n), mean, SD, median, minimum, and maximum.

For categorical/qualitative variables, descriptive statistics will include frequency counts and percentages. The total number of patients in a treatment group will be used as the denominator for percentage calculations, unless stated otherwise.

For time-to-event data with censoring, the Kaplan-Meier (KM) method will be used to summarize the data.

[figure not shown]

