Treatment-emergent Adverse Event

An AE will be considered treatment-emergent if it occurs in the time period starting with the initiation of the first dose of eteplirsen and ending 28 days after the last dose of eteplirsen for eteplirsen-treated patients, or on or after the Week 1 visit date for untreated control patients.

To define treatment emergence for AEs with missing onset or stop date or time, the following additional criteria will be used:

If both start and stop dates for a particular AE are missing, then the AE is considered treatment emergent.

- If onset date for a particular AE is missing, and stop dates falls after the first date/time, then that AE is considered treatment emergent.

- If onset date for a particular AE is the same as the first dose date and the start times missing, and stop dates falls after the first date/time, then that AE is considered treatment emergent.

Treatment-related Adverse Event

A treatment-related AE is any AE reported on the ADVERSE EVENTS eCRF that is marked as definitely related, or probably/possibly related to study drug.

Treatment-emergent Laboratory Abnormality

A treatment-emergent laboratory abnormality will be defined as any laboratory abnormality occurring or worsening after the initiation of eteplirsen dosing and within 28 days of the last dose of eteplirsen for eteplirsen-treated patients or occurring or worsening on or after the Week 1 visit for untreated control patients.

Prior Medication

A prior medication will be any medication taken and completed prior to the first dose of eteplirsen for eteplirsen-treated patients, or before the Week 1 visit for untreated control patients.

Concomitant Medication

A concomitant medication will be any medication that is taken in the time period starting with the initiation of the first dose of eteplirsen dosing and ending 28 days after the last dose of eteplirsen for eteplirsen-treated patients, or on or after the Week 1 visit for untreated control patients.

Previous Drisapersen Exposure Status

A patient will be considered as having previous exposure to drisapersen if he had taken any drisapersen prior to Day 1 in this study (value=Yes); otherwise a patient will be considered as not having a previous exposure to drisapersen (value=No).

Time Since DMD Diagnosis

The time since DMD diagnosis, in months, will be calculated as (Day 1 – Date of DMD diagnosis + 1)/30.4375.

Duration of Corticosteroid Treatment

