7.9.1 Adverse Events

Adverse events will be coded using Medical Dictionary for Regulatory Activities (MedDRA Version 17.1 or higher). This coding system provides five levels to classify AEs. In general, AEs will be presented by system organ class (SOC) and PT but other classifications may be used if warranted.

The sorting order for the AE incidence tables, unless otherwise specified, will be by decreasing frequency in the active treatment arm. Multiple occurrences of the same AE (at the PT level) in the same patient will be counted only once in the frequency tables. If a patient experiences multiple episodes of the same event with different relationship/severity, the event with the strongest relationship or maximum severity to investigational drug product will be used to summarize AEs by relationship and severity. For example, for the table of AEs by SOC and PTs sorted by decreasing frequency presented by treatment group, SOC will be presented in decreasing frequency order of the active treatment column, and within each SOC, PTs will be presented in decreasing order of active treatment column. A patient is counted only once within each SOC and PT.

If a patient experiences multiple events that map to a single PT, the maximal severity grade and strongest investigator assessment of relation to study medication will be assigned to the PT for the appropriate summaries. Should an event have a missing severity or relationship, it will be classified as having a severity of “SEVERE” and/or a “DEFINITELY RELATED” relationship to study medication.

An overall summary of AEs table will be presented which will include:

- Number of Treatment-emergent AEs (TEAEs)
- Number of TEAEs by Severity
- Number of patients with at least 1 TEAE
- Number of patients with at least 1 Severe TEAE
- Number of patients with at least 1 treatment-related TEAE
- Number of patients with at least 1 treatment-emergent SAE
- Number of patients with at least 1 treatment-related, treatment-emergent SAE
- Number of patients with at least 1 TEAE leading to discontinuation of study drug
- Number of patients with a TEAE leading to death

Treatment-Emergent AEs (TEAEs)

The following TEAEs summary tables will be presented by treatment group:

- TEAEs by SOC and PT
- TEAEs by SOC, PT, and severity

- TEAEs by descending frequency of PT
- Treatment-related TEAEs by SOC and PT
- Treatment-related TEAEs by SOC, PT, and severity
- Treatment-related TEAEs by descending frequency of PT

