- TEAEs reported in $\geq 10\%$ of patients in any treatment group (upon examination of the actual data, different cut-off points may be used to examine the incidence of these AEs if it is deemed appropriate)
- TEAEs reported in $\geq 2\%$ of patients in the active treatment group (and greater than untreated group)

The following listings will be produced:

- Listing of non-TEAEs
- Listing of TEAEs
- Listing of TEAEs leading to discontinuation of study drug
- Listing of TEAEs leading to withdrawal from study

Listings will include all data with an indicator for treatment period for each record when the event occurred.

Serious Adverse Events and Deaths

The following summary tables will be produced:

- treatment-emergent nonserious AEs
- treatment-emergent SAEs
- treatment-related, treatment-emergent SAEs
- deaths and AEs resulting in death
- AEs leading to study drug discontinuation by SOC and PT

The following listings will be produced:

- Listing of all AEs
- Listing of AEs leading to discontinuation
- Listing of SAEs (including pre-dosing SAEs)
- Listing of death
- Listing of SAEs that occurred prior to the initiation of study drug or after 28 days post-last dose will be excluded from the tables but will be included in the listing at the start date/time of the AE.
- Listing of AEs related to study procedure by SOC and PT

Listings will include all data with an indicator for treatment period for each record when the event occurred.

A summary of deaths and reasons for deaths will be presented by Analysis period and treatment group. A patient-level listing will be provided.

Adverse Events of Special Interest

Summaries of AEs of special interest will be summarized by SOC and PT. All standardised MedDRA Queries ([SMQs]) listed below will include broad and narrow terms. The AESI are:

- hypersensitivity (hypersensitivity SMQ)
- renal toxicity (acute renal failure SMQ)
- infusion-related reaction (IRR) (AEs occurring within 24 hours of the start of any infusion [including events occurring on the same date as an infusion where infusion start time or AE onset time was not reported])

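### One SAP 7.9.1 table selects adverse-event terms by a crude comparison with control over unequal follow-up, so it tends to over-list no-effect terms on eteplirsen (a minor reporting bias)

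*SAP*

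**What the plan says.** - **Selection rule.** SAP 7.9.1 lists terms reported in at least 2% "of patients in the active treatment group (and greater than untreated group"). It is the only adverse-event table listed there whose content is decided by comparing treated with control.
- **Counting.** "A patient is counted only once within each SOC and PT" (SAP 7.9.1). "The total number of patients in a treatment group will be used as the denominator for percentage calculations", unless stated otherwise (SAP 6.1). Nothing different is stated for this table.
- **Treated window.** It starts at the first dose, "ending 28 days after the last dose of eteplirsen for eteplirsen-treated patients" (SAP 6.7), with no cut at Week 96. Dosing lasts 96 weeks plus an optional extension: "Patients may continue in the safety extension for up to 48 weeks", ending sooner on commercial availability or transfer to another study (Protocol Section 2, Table 4, footnote a).
- **Control window.** It starts at the Week 1 visit (SAP 6.7). Controls "will complete selected study assessments through 96 weeks" (SAP 4.1). After early discontinuation, their events are recorded only through the Early Termination visit (Protocol 11.1). SAP 4.4.2 refers to the "large dropout rate of the untreated control group", and SAP 7.8 calls it high.
- **Data cut.** The final analysis follows the last patient's completion of the whole study (SAP 4.4.2), so extension events are included.
- **Partial handling.** Adverse-event listings carry a treatment-period indicator and deaths are summarised by analysis period (SAP 7.9.1). Weeks on study are summarised by group (SAP 7.1), as is duration on eteplirsen (SAP 7.7). The SAP does not say that any of these is applied to the treatment-emergent event tables.

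**The concern.** The proportion of patients who have ever had an event rises with the time they are watched. If one group is watched longer, its crude percentage is higher even when the underlying hazards are equal. A filter that keeps only terms with a higher percentage on treatment then favours terms that differ only in follow-up.

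A list built this way invites the reader to take its contents as events associated with the drug. What is at stake is how that one list is interpreted. The recorded events and the complete tables are unaffected.

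**Working it through.** **1. Length of follow-up.** The protocol synopsis states "Total patient participation: approximately 158 weeks". This reproduces as 10 (screening) + 96 + 48 + 4 = 158. Follow-up from Week 1 is thus at most 96 + 48 + 4 = 148 weeks, which matches the Week 148 End of Study visit. The control maximum is about 96 weeks, and 148/96 = 1.54. If no treated patient uses the extension, treated follow-up is 96 + 4 = 100 weeks.

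**2. Inputs.** Planned sizes (SAP 4.2) are 70 + 10 = 80 treated and 20 + 10 = 30 control. Two per cent of 80 is 1.6, so a term needs at least 2 treated patients. The documents give no event rates, extension use or dropout rates. Assumed: the same constant rate in both groups, 0.03 to 0.2 per patient-year. Unless stated, no treated dropout.

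**3. Formulas.** Risk over w weeks is p = 1 − exp(−rate × w/52.18). The chance that a no-effect term is listed is the sum over treated counts x ≥ 2 of Binomial(x; 80, p_treated) × P(control count/30 < x/80).

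Example at 0.1 per patient-year: p is 24.7% at 148 weeks and 16.8% at 96 weeks. The listing chance is 0.82, against 0.50 when both groups have 96 weeks.

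**4. Results over the rate range.**

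| Weeks, treated vs control | Chance a no-effect term is listed |
|---|---|
| 96 vs 96 | 50–52% |
| 100 vs 96 (extension unused, controls complete) | 52–54% |
| 120 vs 96 | 61–72% |
| 148 vs 96 (extension fully used) | 71–89% |
| 100 vs 69 (assumed 50% control dropout) | 66–82% |
| 80 vs 69 (treated dropout as well) | 56–63% |
| 148 vs 96, assumed 10 controls | 64–78% |

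The 69 weeks is mean control follow-up with exponential dropout reaching 50% at Week 96: 0.5 × 96/ln 2 = 69.2. For rarer terms the 2% threshold also matters. At a 2% risk over 96 weeks, the chance is 33% at equal follow-up and 54% at 148 versus 96.

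**5. Early events.** In a simulation with treated patients followed for 148 weeks and 50% control dropout, a no-effect term confined to the first 12 weeks (10% in each group) passes the crude comparison 53% of the time. That is close to chance.

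**6. What Kaplan-Meier incidence adds.** In the same scenario, with rates 0.03/0.1/0.2, the SAP rule lists 81/94/98% of no-effect terms. A comparison on Kaplan-Meier incidence at Week 96 passes 52/52/51%. By subtraction, about 0.939 − 0.521 = 0.42 of no-effect terms at rate 0.1, and 0.983 − 0.511 = 0.47 at rate 0.2, exceed control on the crude percentage but not on Kaplan-Meier incidence.

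**7. What a Week-96 cut would do.** In that scenario a cut alone still lists 64/74/81%, because it does not address control dropout. It also loses real rare reactions. For a reaction absent in controls, the listing chance is P(at least 2 of 80). At 0.01 per patient-year, risk is 2.8% over 148 weeks and 1.8% over 96, and the chance falls from 66% to 43%. At 0.02 it falls from 94% to 79%.

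**The case against.** The strongest reply is that this is one display filter in a descriptive safety section. SAP 6.3 and 8.1 rule out inferential comparison with the untreated group. The error adds terms and removes none. Treatment-related tables and the medically reviewed infusion reactions do not pass through the filter. Even at equal follow-up about half of no-effect terms pass, so the list never identified drug effects. Summaries of weeks on study and of duration on eteplirsen let a careful reader see the imbalance. All of this stands, and it keeps the point minor.

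It does not remove the point. A descriptive filter can still be biased, and SAP 7.8 itself says that dropout makes treated-versus-control comparison not meaningful for efficacy. This table nevertheless uses such a comparison to choose its content.

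It is also fair to object that the largest figures need full use of the extension and no treated dropout, and that a constant hazard is assumed. That stands too. If the extension is unused and controls complete, the excess over equal follow-up is only 2–4 points.

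A reader might infer that safety signals are being lost, or that the side-by-side tables should all be cut at Week 96. The documents do not support the first: unfiltered tables by system organ class and preferred term are planned. The second would remove the whole-study tables that provide this protection. It would also leave events in Weeks 96 to 100 without a table for patients who skip the extension.

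**Conclusion.** The point holds as a minor reporting bias. For events that accrue over time, the filter over-lists no-effect terms on eteplirsen whenever treated patients are observed longer than controls. The chance of listing rises from about 50% to 52–54% at 100 versus 96 weeks, and to 71–89% at the 148-week ceiling against 96. These figures rest on the planned group sizes, a constant hazard, no treated dropout and the assumed rates. Treated dropout and fewer controls both shrink the excess.

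The upper range should not be read as the expected result. The documents do not say how many patients use the extension or how many drop out.

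**What to change.** In SAP 7.9.1, keep all whole-study treatment-emergent event tables and the existing selection rule, so that no term is dropped. For the filtered table, and preferably also for the table by system organ class and preferred term:

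1. Add, by group, patient-years at risk, exposure-adjusted incidence (patients with a first event per 100 patient-years) and Kaplan-Meier cumulative incidence at Week 96. Censor each patient at the end of his treatment-emergent window, which for controls is the last assessment.
2. Mark terms that exceed control on the crude percentage but not on Kaplan-Meier incidence at Week 96.
3. Add a footnote that follow-up is unequal and that the list must not be read as drug-associated events.

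**Cost.** SAP wording and a few extra columns, from data already collected. With very few controls the Kaplan-Meier estimate is imprecise, and about half or more of no-effect terms still pass by chance. With an assumed 10 controls, 50% control dropout and a rate of 0.03, about 62–63% pass. Kaplan-Meier assumes that dropout is unrelated to the event. Differences in visit frequency, infusions and biopsies are not removed.

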9.7. Prior and Concomitant Medications and Therapeutic Procedures

For both treatment groups, the dosing regimen for oral corticosteroids for treatment of DMD including, but not limited to, prednisolone, prednisone, or deflazacort, should be kept the same throughout the study except for modifications to accommodate changes in weight.

For both treatment groups, the following therapies may be used before enrollment and throughout the study; however, the dosage should be constant throughout the treatment period, unless clinically indicated:

- Oral ACE inhibitors, including but not limited to perindopril and lisinopril
- Oral β-blockers, including but not limited to carvedilol and atenolol
- Angiotensin-receptor blockers, including but not limited to losartan, irbesartan, valsartan, and candesartan
- Oral laxatives, including but not limited to lactulose, Senokot, and Movicol
- Vitamin D and calcium supplements
- Alendronate (Fosamax) or other bisphosphonates used to treat osteoporosis/osteopenia by inhibiting osteoclasts

• Over-the-counter herbal preparations, including herbal supplements, vitamins, minerals, and homeopathic preparations, provided the patient had been on stable doses for 24 weeks before enrollment in this study

Recommendations for selection of medications and interventions during anesthesia include:

- The use of depolarizing muscle relaxants such as succinylcholine are not permitted in any case due to their potential to induce rhabdomyolysis in patients with DMD
- Volatile anesthetics should be avoided if possible, also due to a risk of rhabdomyolysis

Other concomitant medications (e.g., vitamins or other non-RNA antisense medications) may also be taken if, in the opinion of the Investigator, they do not interfere with study assessments and outcomes. Every attempt should be made to keep the dosage constant throughout the study treatment period (i.e., through Week 96).

Introduction of new physiotherapy interventions during the course of the study must be avoided unless the best interests of the patient are at risk. Should a contracture develop during the course of the study, and it is considered in the best interest of the patient to treat the contracture, then any of the following interventions may be used to reduce the contracture, but they must be clearly documented:

- Contracture control devices
- Night splints
- Stretching exercises (passive, active, self)
- Serial casting

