10.2.2. Baseline Period (3-5 Weeks after Screening Functional Assessment Visit)

The muscle biopsy should be the last Baseline procedure performed.

At Hub Sites (Baseline Functional Assessment Visit; occurs within 4 weeks prior to Week 1):

The Baseline period may require a 2-night overnight stay near the Hub Site. Assessments will begin in the mornings on Day 1 and Day 2 in the order described in the Clinical Evaluator Manual.

Day 1:

- Assess eligibility
- Vital signs
- Height and ulnar length
- CCI
- 6MWT (Pulse will be recorded immediately prior to and after the 6MWT.)
- NSAA
- CCI

Day 2:

- CCI
- 6MWT (Pulse will be recorded immediately prior to and after the 6MWT.)
- NSAA
- CCI

Either Day 1 or Day 2:

• ECG

At Surgical Units (After eligibility has been confirmed) (for the treated group only):

The muscle biopsy should be the last Baseline procedure performed after the Local Site has confirmed eligibility. Assessments at the Surgical Unit should be performed in the order described in the Clinical Evaluator Manual.

- Informed Consent
- Safety laboratory assessments, including chemistry, hematology, coagulation, and urinalysis
- Immunogenicity
- A muscle biopsy will be performed on all patients in the treated group. The biopsy may be obtained as soon as eligibility is confirmed (i.e., Baseline assessment is complete and genotype is confirmed), prior to the first dose of eteplirsen. The first dose of eteplirsen must be within 4 weeks of the Baseline Functional Assessment visit. Surgery must be performed within the 4-week window between the Baseline Functional Assessment visit and Week 1. Patients in the treated group may not begin to receive eteplirsen until after the Baseline muscle biopsy has been performed.

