11. ADVERSE EVENTS

11.1. Collection of Adverse Events

Over the entire duration of the study, site personnel will ensure that all AEs are recorded appropriately. If an AE occurs, the primary concern is for patient safety, and the Investigator will use their judgment and expertise to determine the appropriate course of action.

All AEs from the time of informed consent through the End of Study visit (or early termination from the study) will be recorded in each individual patient's CRF. For patients who prematurely discontinue the study (see Section 9.4.2), AEs will continue to be recorded until 4 weeks after the last eteplirsen infusion for the randomized group or through the Early Termination visit for the untreated control group.

If, at any time after the patient has completed participation in the study (see Section 9.4.2), the Investigator or study staff becomes aware of an SAE that the Investigator believes is possibly/probably or definitely related to the IP (Section 11.3.1) or is possibly/probably or definitely related to a study procedure (Section 11.3.2), then the event and any known details must be reported promptly to the Sponsor.

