13.10.2.1. Adverse Events

For treated patients, only TEAEs will be summarized. Non-treatment emergent events will be recorded in data listings. For all AE tables, the number and percent of patients reporting AEs (grouped by MedDRA SOC and PT) will be summarized by treatment group. In general, tables will have events categorized into all TEAEs and treatment-related TEAEs.

As untreated patients (control group) will have no TEAEs, AEs collected post-qualification for the study will be summarized similarly to treated patients' TEAEs. All captured AEs for this control group will be listed.

Multiple occurrences of the same AE (at the PT level) in the same patient will be counted only once in frequency tables. If a patient experiences multiple episodes of the same event with different relationship/severity, the event with the strongest relationship and maximum severity to IP will be used to summarize AEs by relationship and severity. Treatment-related TEAEs will be defined as those that the Investigator considers possibly/probably or definitely related to the IP.

The following summary tables will be produced:

- TEAEs
- TEAEs by severity
- Treatment-related TEAEs
- Treatment-related TEAEs by severity
- SAEs

In addition, all SAEs, regardless of their treatment-emergent status will be summarized by SOC and PT.

The following listings will be produced:

- Non-treatment emergent AEs
- All TEAEs
- AEs leading to discontinuation
- SAEs

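### The SAP omits the protocol's table of all SAEs, so serious events of the pre-dose Baseline biopsy are listed but not counted in any SAE frequency table

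*SAP*

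**What the plan says.** Protocol 13.10.2.1 opens with a general rule for adverse events: "For treated patients, only TEAEs will be summarized. Non-treatment emergent events will be recorded in data listings". It then makes an exception for serious events: "In addition, all SAEs, regardless of their treatment-emergent status will be summarized by SOC and PT". It also asks, separately, for a listing of SAEs.

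SAP 7.9.1 plans two SAE tables, one of treatment-emergent SAEs and one of those that are also treatment-related. The SAE counts in its overall AE summary are likewise treatment-emergent. It then says "Listing of SAEs that occurred prior to the initiation of study drug or after 28 days post-last dose will be excluded from the tables", and the sentence continues "but will be included in the listing at the start date/time of the AE".

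The windows differ. Protocol 13.10.1 counts an event as treatment-emergent up to 30 days after the last administration; SAP 6.7 stops at 28 days.

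On the biopsy, Protocol 10.2.2 says "Patients in the treated group may not begin to receive eteplirsen until after the Baseline muscle biopsy has been performed". Protocol 11.1 collects adverse events from informed consent, and Protocol 11.3.2 has the investigator classify each for relationship to study procedures.

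**The concern.** The protocol's sentence on SAEs matters only for events outside the treatment-emergent window, because events inside it are already tabulated under the general rule. The SAP's exclusion removes exactly those events from the tables. The two instructions cannot both be followed.

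The events most clearly affected are those of the Baseline biopsy, a surgical procedure that every treated boy must undergo before his first dose. A complication that begins before dosing is non-emergent by definition, however serious. The second biopsy, at Week 24, 48, 72 or 96, falls in the treatment period, so its SAEs would normally be tabulated. Half of the planned biopsies would therefore be covered by the SAE tables and half would not, at least for complications that begin before dosing.

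At stake is how completely the tables describe serious events in a paediatric trial. Readers of a study report usually take SAE frequencies from the tables and not from the listings. The efficacy conclusions are not touched.

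**Working it through.** The plan gives no figure to reproduce. The check compares the two texts and adds one illustration of size.

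**Step 1. Where each kind of SAE in a treated boy goes**

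| Onset | Protocol 13.10.1 and 13.10.2.1 | SAP 6.7 and 7.9.1 |
|---|---|---|
| Consent to first dose | All-SAE table by SOC and PT, plus listing | Listing only |
| First dose to day 28 after last dose | Tabulated | Tabulated |
| Days 29–30 after last dose | Treatment-emergent, tabulated | Not treatment-emergent, listing only |
| After day 30, if recorded | All-SAE table, plus listing | Listing only |

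The windows differ by 30 − 28 = 2 days.

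**Step 2. Does a listing satisfy the protocol?** No. Protocol 13.10.2.1 asks for the summary by SOC and PT and for an SAE listing as separate outputs.

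**Step 3. Is the change declared?** Protocol 13.1 says that departures from the protocol's analyses will be included in the SAP. The readable bullets of SAP 8.1 cover the dropped comparison with controls, the reduced by-visit safety summaries and the renaming of a label. None mentions SAE tabulation or the 28-day window. Two bullets are redacted, so the finding is only that no visible entry declares it.

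**Step 4. Size of the pre-dose group**

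- Planned treated boys (Protocol synopsis): about 70 with Baseline 6MWT of 300 to 450 m, plus about 10 above 450 m. 70 + 10 = 80.
- One Baseline biopsy each: about 80. One later biopsy each: about 80. Total about 160, so 80/160 = half are pre-dose.
- Risk r of an SAE with onset between biopsy and first dose: not in the documents, so assumed.
- Expected number = 80 × r. Chance of at least one = 1 − (1 − r)^80.

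| Assumed r | Expected SAEs | Chance of at least one |
|---|---|---|
| 0.25% | 0.2 | 18% |
| 0.5% | 0.4 | 33% |
| 1% | 0.8 | 55% |
| 2% | 1.6 | 80% |
| 3% | 2.4 | 91% |

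The contradiction in Step 1 holds whatever r is.

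**Step 5. Size of the late group.** For treated boys who discontinue early, Protocol 11.1 records adverse events until 4 weeks after the last infusion: 4 × 7 = 28 days. The synopsis also gives a 4-week safety follow-up. Routine recording therefore ends about where the SAP's window ends. After participation, an SAE believed related to the drug or a study procedure must still be reported: "then the event and any known details must be reported promptly to the Sponsor". That sentence does not say that the event enters the case report form. The late group is the few SAEs recorded after day 28 plus any later related SAE that reaches the database.

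**Step 6. Denominator.** SAP 5.3 admits a treated-group boy to the Safety Set only after at least one dose, and SAP 7.9 bases the safety analyses on that set. A boy who has a biopsy SAE and is never dosed would be missing even from a restored table built on the Safety Set.

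**The case against.** The strongest reply is that nothing is hidden. SAP 7.9.1 plans a listing of SAEs that expressly includes those before dosing, listings of all adverse events and of non-emergent ones, and a listing of procedure-related events. Listings carry a treatment-period indicator. The exclusion is stated openly in the SAP. Pre-dose events cannot be caused by eteplirsen, and the safety objective is the safety and tolerability of eteplirsen. All safety analyses are descriptive.

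Much of this stands, and it rules out several stronger readings that a reader might infer:

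- *That these SAEs are lost or go entirely uncounted.* They remain in patient-level listings. A fatal event may appear in the summary of deaths by analysis period. The summaries of events of special interest and of additional events, which include haemorrhage terms, are not expressly limited to treatment-emergent events. What is missing is a count in an SAE frequency table.
- *That many late drug-related SAEs are dropped.* Step 5 shows why the documents do not establish this.
- *That biopsy SAEs are to be expected.* Protocol 9.7 bars depolarizing muscle relaxants "due to their potential to induce rhabdomyolysis in patients with DMD". This is a precaution on anaesthesia and gives no biopsy risk.
- *That the change was made without declaration.* The redacted bullets in SAP 8.1 prevent that conclusion.

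The reply does not remove the contradiction. The protocol promised a summary as well as a listing, and its exception for SAEs is not limited to events that the drug could have caused.

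**Conclusion.** The concern holds as a direct conflict between Protocol 13.10.2.1 and SAP 7.9.1. If the SAP is followed as written, SAEs of the Baseline biopsy with onset before dose 1 appear in no SAE frequency table. About 80 planned biopsies are exposed to this. How many events are affected is unknown: the range of 0.2 to 2.4 expected SAEs rests entirely on assumed rates of 0.25% to 3%. It would therefore go too far to say that the tables will understate harm; they would do so only if such an event occurs.

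The secondary consequence, for SAEs on days 29–30 and for later related SAEs that reach the database, is real but probably small.

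This should be corrected before reporting. It concerns the completeness of safety tabulation and does not alter any efficacy result.

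**What to change.** 1. In SAP 7.9.1, restore the protocol's table of all SAEs by SOC and PT, whether or not treatment-emergent. At a minimum, separate onset before dosing, during treatment and after the window, and show relationship to study procedure. The protocol requires only the single table; the split is recommended so that biopsy events are not read as drug effects.
2. Use enrolled or biopsied boys as the denominator for the pre-dose part, so that a boy biopsied but never dosed is included.
3. Confine the exclusion sentence to the treatment-emergent tables.
4. Reconcile the 28-day and 30-day windows, and record the outcome in SAP 8.1.

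If the sponsor prefers not to restore the table, SAP 8.1 should declare and justify its omission.

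The cost is minor wording and one more table. Pre-dose SAEs and their relationship to procedures are already recorded from consent. The post-window rows can include only what has reached the database. The total SAE count may look slightly less favourable.
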